9.6. Sponsor Responsibilities

Sponsor has the overall responsibility of the study and will:

 neuroloop	Confidential	Protocol – The baroloop Study
--	---------------------	-------------------------------------

- Select qualified Principal Investigators, clinical investigators and study sites
- Select qualified monitors
- Provide the Investigational Plan and any subsequent amendments
- Provide appropriate information and baroloop System training to Investigators and study site staff
- Ensure that all deviations from the Investigational Plan are reviewed with the appropriate Investigator(s) and reported in the data collection system and the final report and that any necessary preventative or corrective action is taken
- Ensure that all adverse events and all adverse device effects (ADEs) are reported and reviewed with the Investigator(s), and where appropriate, that all serious adverse events (SAEs) and all serious adverse device effects (SADEs) are appropriately reported
- During the course of the investigation, inform in writing all Investigators about adverse events and adverse device effects that have been reported to Sponsor (this information shall be sent to each Investigator based on perceived risk)
- Promptly inform the Investigators and where applicable, any regulatory authorities, if the study is prematurely terminated or suspended and the reason for the termination or suspension
- Ensure proper device usage, uniform data collection and protocol compliance
- Provide protocol initiation training to include review of the baroloop system instructions for use, the Investigational Plan, entry of complete data into the data collection system, and guidelines for obtaining informed consent
- Provide the baroloop System to participating study sites, in quantities to support study activities
- Coordinate ongoing communication with CRO(s), consultants and study sites to resolve any problems concerning the protocol or data collection
- Every effort will be made to ensure compliance with the protocol
- Retain ownership of all clinical data generated in this study, and control the use of the data for purposes of regulatory submissions to CAs
- Protect subject confidentiality

A description of this clinical study will be made available on <http://clinicaltrials.gov>.

9.7. Monitor Responsibilities

The Sponsor has contracted MAXIS Medical as the Clinical Monitor to support the Sponsor in implementing and monitoring the clinical investigation until its termination. Clinical monitors, qualified by training and experience, will be responsible for monitoring and overseeing the conduct of the trial.

Clinical monitors will conduct site initiation visits at each investigational site to ensure that the Principal Investigator and other investigational site personnel involved in the conduct of this investigation have received and understood the requirements and contents of the clinical investigational protocol, the Investigators Brochure, the patient informed consent form, the data collection system, the Instructions for Use and the institution and / or Investigator agreement.

Clinical monitors will ensure that the site facilities are adequate for the conduct of this investigation and that resources, laboratories, equipment and personnel remain adequate throughout the investigation.

The clinical monitors will conduct routine on-site monitoring visits and phone calls to evaluate compliance with the protocol, any specific recommendations made by the site's Ethics Committee (EC) and the signed Institution and/or Investigator Agreement and to ensure that the protocol is being followed and that any protocol deviations are properly documented on respective form. Clinical monitoring will include a verification that Informed Consent Form was properly obtained for all enrolled trial participants, a review of clinical records for accuracy and completeness, resolution of missing or inconsistent results and a review of source documents.

Clinical monitoring will include a review of all adverse events and device malfunctions to ensure that all information has been reported to the sponsor, EC and regulatory authorities as required by this investigational plan and applicable standards and laws.

The clinical monitor will verify that the information in the data collection system is complete and in agreement with the source documentation and other records. The clinical monitor will ensure that data has been entered into the data collection system and is signed and dated by the investigator.

The Investigator will make available to the clinical monitor for review all Informed Consent documents, all completed information in the data collection system, source documentation and other relevant records for all enrolled subjects at the site. It is important that the Investigator and other relevant site personnel are available for consultation with the clinical monitors during the monitoring visits and that sufficient time is devoted at the site for the monitoring process.

If a deficiency is noted during an on-site visit or at any other time during the course of the trial, the clinical monitor is required to discuss the situation with the Investigator and the Sponsor, and to subsequently monitor the implementation of corrective actions that are required to address the situation.

All monitoring activities will be documented by the clinical monitor and will include, at a minimum, the date, investigational site visited, names of all personnel involved in the visit, a listing of all documents reviewed and a summary of all findings, facts, deviations conclusions and recommended actions to be taken. Key findings will be reviewed with the clinical investigator.

Upon completion of the study, a study close out visit will be conducted to ensure that all data collection and study requirements are complete.

9.8. Investigator Responsibilities

At a minimum, the following documents will be provided by the investigational site to the Sponsor prior to study start (consent of the first subject):

- Signed Clinical Trial Agreements
- Signed Financial Disclosure Form
- Signed Clinical Investigational Plan Signature Page
- Relevant regulatory approvals
- Investigator and Co-Investigator's current Curriculum Vitae
- Any other additional documents as required by the Sponsor

 neuroloop	Confidential	Protocol – The baroloop Study
--	---------------------	-------------------------------------

The Investigator is responsible for ensuring that the investigation is conducted according to all signed agreements, the study protocol, governing regulations, data protection regulations, the Declaration of Helsinki and any other conditions imposed by the relevant regulatory authorities. The Investigator is responsible for maintaining medical and study records for every subject participating in the clinical study (including information maintained electronically such as digital imaging). The Investigator will also maintain original source documents from which study-related data are derived.

The Investigator(s) shall be responsible for the day to day conduct of the investigation as well as for the safety and well-being of the human subjects involved in the clinical investigation.

The Investigator(s) shall:

- Have the resources to conduct the investigation properly
- Ensure that conducting the investigation will not give rise to a conflict of interest
- Obtain from the Sponsor the information which the Investigator(s) judges essential about the device and be familiar with this information
- Be well acquainted with the Clinical Investigation Protocol (CIP) before signing the signature page
- Support the monitor, auditor, if applicable, in their activities to verify compliance with the CIP, to perform source data verification and to correct the information in the data collection system where inconsistencies or missing values are identified
- Discuss with the Sponsor management any question of modification of the CIP
- Make sure that the CIP is followed by all responsible for the conduct of the study at his / her institution. Any deviation shall be documented and reported to the study Sponsor
- Make the necessary arrangements to ensure the proper conduct and completion of the investigation
- Make the necessary arrangements for emergency treatment, as needed, to protect the health and welfare of the subject
- Ensure that appropriate regulatory approval is obtained prior to the start of the investigation
- Provide regulatory approvals to the Sponsor
- Inform Sponsor about adverse events in a timely manner
- Endeavor to ensure an adequate recruitment of subjects
- Ensure that the subject has adequate information to give informed consent
- Ensure that informed consent is obtained and documented
- Ensure that clinical records are clearly marked to indicate that the subject is enrolled in this study
- Provide subjects with well-defined procedures for any emergency situation and safeguard the subject's interest. Under these circumstances, deviations from the CIP shall not require the prior approval of the Sponsor or the national and local regulatory authorities. Such deviations shall not be considered as a breach of agreement but shall be documented and reported to Sponsor
- Ensure that information which becomes available as a result of the clinical investigation which may be of importance to the health of a subject and the continuation of the

 neuroloop	Confidential	Protocol – The baroloop Study
--	---------------------	-------------------------------------

investigation shall be made known to the Sponsor and, if pertinent to the safety or well-being of the subject, and the private clinician

- Inform the subject and / or the subject's physician about any premature termination or suspension of the investigation with a rationale for study termination
- Have primary responsibility for the accuracy, legibility and security of all investigation data, documents and subject records both during and after the investigation
- Sign each subject's data in the data collection system, as applicable
- Be responsible for the supervision and assignment of duties at his / her clinical center
- Ensure that all investigational devices are kept in a secure location and that all Systems are accounted for (number of devices used, discarded and returned to Sponsor)

9.9. Study Funding

This clinical investigation is fully funded by the Sponsor. The Sponsor will enter into clinical research / clinical trial agreements with all clinical sites participating in the study. Comparable research agreements will be executed with core laboratories or other contributors in this clinical investigation, if applicable.

9.10. Investigator Training

The baroloop System is intended for use by experienced physicians. A limited number of Investigators at each site will be authorized to use the study device. These Investigators will be trained by Sponsor personnel (or designated representative) in a didactic session using a 'briefing checklist' to make sure that all user-related, risk mitigations for the baroloop System are fully understood by each investigator.

9.11. Medical Monitor

A Medical Monitor will be responsible for overseeing the overall progress of the protocol. The Medical monitor will review patient recruitment, any Serious Adverse Events, any Unanticipated Adverse Events, and non-compliance with the protocol at individual centers. All Serious Adverse Events will be reviewed and adjudicated by the Medical Monitor.

9.12. Data Management

Investigators are responsible for the accurate completion and timely submission of the data collected during the trial. All data from the trial will be entered into a data collection system. Incoming data will be frequently reviewed to identify inconsistent or missing data and any adverse events. Any data issues are to be promptly addressed with the Investigator by the CRO (MAXIS Medical). By quality assurance procedures it is ensured that complete, accurate and timely data are submitted; that protocol requirements are followed; and that complications, adverse events and adverse device effects are correctly reported and investigated, as appropriate.

9.13. Study Suspension or Early Termination

The study will be terminated early if the DSMB determines at any time during the study that the composite MAE rate is unacceptably high. Furthermore, the study will be terminated early if the number of failures to implant the devices exceeds 4 (four) failures.

The study can be discontinued at the discretion of the Investigator or study Sponsor for reasons including, but not limited to, the following:

 neuroloop	Confidential	Protocol – The baroloop Study
--	---------------------	-------------------------------------

- Occurrence of adverse events unknown to date in respect to their nature, severity, or duration, or the unexpected incidence of known adverse events
- Obtaining new scientific knowledge that shows that the study is no longer valid or necessary
- Insufficient recruitment of subjects
- Unanticipated adverse device effect (UADE) presenting an unreasonable risk to subjects (Sponsor may terminate the study immediately)
- Persistent non-compliance with the protocol
- Persistent non-compliance with regulatory requirements

If the study is discontinued or suspended prematurely, the Sponsor shall promptly inform all clinical investigator(s) / investigational center(s) of the termination or suspension and the reason(s) for this. The national and local regulatory authorities shall also be informed promptly and provided with the reason(s) for the termination or suspension by the Sponsor or by the clinical Investigator / investigation center(s).

9.14. Criteria for Suspending / Terminating a Study Center

Sponsor reserves the right to stop the screening of subjects at a study center at any time after the study initiation visit if no subjects have been enrolled or if the center has multiple or severe protocol violations without justification or fails to follow remedial actions.

Possible reasons for suspending / terminating a study center include, but are not limited to:

- Repeated failure to complete case report forms prior to scheduled monitoring visits;
- Failure to obtain written Informed Consent;
- Failure to report SAEs / UADEs to Sponsor within 24 hours of knowledge;
- Loss of (or unaccounted for) investigational product inventory.

9.15. Final Report

A Final Report will be prepared even if the study is prematurely terminated. The Final Report will be submitted to each participating Investigator, and regulatory agencies, as required.

9.16. Protocol Deviations

A protocol deviation is defined as an event where the Investigator or site personnel did not conduct the study according to the protocol.

Investigators shall be required to obtain prior approval from Sponsor or its designated representative before knowingly deviating from the protocol, except where necessary to protect the life or physical well-being of a subject in an emergency. Such approval shall be documented in writing and maintained in clinical study management and Investigator files. Prior approval is generally not expected in situations where unforeseen circumstances are beyond the Investigator's control, (e.g., subject was not available for scheduled follow-up office visit, blood sample lost by laboratory, etc.); however, the event is still considered a deviation and will be reported in the data collection system.

Deviations must be reported to Sponsor or designated representative regardless of whether medically justifiable, pre- approved by Sponsor or designated representative, or taken to protect the subject in an emergency. Subject specific deviations will be reported on the Protocol

Deviation case report form. Non-subject specific deviations, (e.g., unauthorized use of an investigational device outside the study, unauthorized use of an investigational device by a physician who has not signed an Investigator agreement or not been trained in the use of the device, etc.), will be reported to Sponsor or designated representative. Investigators will also adhere to procedures for reporting study deviations to their Ethics Committee or Competent Authority, where required, in accordance with their specific reporting policies and procedures.

Regulations require that Investigators maintain accurate, complete and current records, including documents showing the dates of and reasons for each deviation from the protocol.

10. Regulatory Considerations

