4.31. Unscheduled Follow-up Visit

If an unscheduled follow-up visit is required, the study subject should be assessed for new or unresolved adverse events. Any testing required, including imaging studies, should be provided to the study Sponsor for DSMB adjudication. Office cuff blood pressure will be taken

and will be reviewed. Change of medications, diagnostic test results, or interventions should be documented.

4.32. 4.32 Schedule of Study Visits and Assessments

Table 3: Schedule of Study Visits and Assessments

Visit	Follow-up									Long Term Follow-up
	Visit 1	Visit 2	Visit Procedure	Discharge	14 Days (+/- 3 days)	Weekly Office visits (1x/2x)*	30 Days (+/- 7 days)	90 Days (+/- 14 days)	180 Days (+/- 14 days)	
Eligibility	✓	✓	✓							
Informed Consent	✓									
Medical History	✓									
Physical Examination	✓		✓		✓		✓	✓	✓	✓
Concomitant medications	✓	✓	✓		✓		✓	✓	✓	✓
Baseline 12 lead ECG	✓									
Blood Testing	✓			✓						
24 hour ABPM		✓					✓	✓	✓	✓
Medication compliance testing		✓					✓	✓	✓	✓
Quality of Life SF-36	✓	✓					✓	✓	✓	✓
neuroloop implantation			✓							
neuroloop titration*,**					✓	(✓)	✓	✓	✓	✓
IPG recharging and data downloading*					✓	✓				
Office cuff BP Measurement	✓	✓	✓	✓	✓	✓	✓	✓	✓	✓
Discharge				✓						
Adverse Events	✓	✓	✓	✓	✓	✓	✓	✓	✓	✓

*Titration after Day 14 takes place 1x per week. The second weekly visit through Day 30 is for Office BP and IPG battery charging only. After Day 30, only one visit per week for charging and (if necessary) titration is required.

**The heart rate and blood pressure will be recorded using a Finapres device during each titration.

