4.35 Study Exit or Premature Withdrawal

Subjects will be exited from the study by completion of a Study Exit form in the data collection system at the time of study completion provided the subject has not experienced an adverse event that is ongoing and unexplained.

Subjects may be terminated or withdrawn from the study early for, including but not limited to, the following reasons:

- Subject death.
- Voluntary withdrawal – meaning that the subject voluntarily chooses not to further participate in the study.
- Lost to follow-up – meaning that the subject is more than 14 days late to a study visit and 3 documented attempts to contact the subject are unsuccessful. A subject who misses a study visit but attends a subsequent visit will no longer be considered lost to follow-up. A missed visit will be considered a protocol deviation and the deviation will be documented and reported.
- In the physician's opinion, it is not in the best interest of the subject to continue study participation.

All subjects enrolled (including those withdrawn or lost to follow-up) shall be accounted for and documented.

5. Risk Benefit Assessment

Sponsor has conducted an analysis of the benefits and risks of the baroloop System and procedures necessary for implantation and use of the baroloop System. A detailed Risk Assessment has been completed, and the conclusion of this review is that this investigational study is justified because the overall potential benefit to the population outweighs its attendant risks.

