6.1. Overview

The primary objective of this study is to characterize the safety and feasibility of the baroloop System in subjects with uncontrolled or resistant hypertension. All subjects will be followed on an intent-to-treat basis (ITT). The device performance will also be assessed based on a per-protocol analysis of the primary safety and feasibility endpoints and secondary efficacy endpoints. An intent-to-treat analysis, along with other secondary analyses, will also be completed and reported.

This is not a hypothesis driven study, and no formal power analysis or hypothesis-driven statistical analysis has or will be performed. Standard summary statistics will be calculated for all study variables. For continuous variables, statistics will include means, standard deviations, medians and ranges. Categorical variables will be summarized using frequency distributions.

The primary endpoints will be analyzed on an intent-to-treat (ITT) basis, for which data from all subjects enrolled will be included. In order to evaluate a true treatment effect, the primary analysis will include those subjects achieving technical success, the definition of which includes successful completion of the study procedure.

If there are no more than 4 failures to implant, combined with a safety level that is determined by the independent DSMB to be acceptable, together with any reduction in blood pressure as a result of the baroloop therapy, this will be considered a successful outcome to this First-in-Human study.

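### Section 6.1 plans a per-protocol analysis of the MAE and feasibility endpoints without defining the set, so subjects could be left out because of the harm or implant failure being counted

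*Combined protocol and SAP*

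**What the plan says.** Section 6.1 states: "The device performance will also be assessed based on a per-protocol analysis of the primary safety and feasibility endpoints and secondary efficacy endpoints". This is the only mention of a per-protocol analysis. Sections 6.2 to 6.6 and the Definitions in section 12 do not say which departures exclude a subject, who decides, or when.

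Section 6.1 describes the other analysis sets in three ways:
- An intent-to-treat analysis is listed together with other secondary analyses.
- The primary endpoints are to be analysed by intent-to-treat in all enrolled subjects.
- The primary analysis is to include the subjects who achieve technical success.

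Departures are described in 9.16: "A protocol deviation is defined as an event where the Investigator or site personnel did not conduct the study according to the protocol". The examples outside the investigator's control are "subject was not available for scheduled follow-up office visit, blood sample lost by laboratory, etc", and for these "the event is still considered a deviation and will be reported in the data collection system". Deviations are reportable even when "pre- approved by Sponsor or designated representative, or taken to protect the subject in an emergency". Section 4.35 adds: "A missed visit will be considered a protocol deviation and the deviation will be documented and reported". Section 9.14 speaks of severe violations, but only as a ground for stopping a centre, and without a definition.

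The contact schedule is dense. Visits are twice weekly early in titration, and the footnote to Table 3 (section 4.32) then says: "After Day 30, only one visit per week for charging and (if necessary) titration is required".

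**The concern.** A per-protocol rate is informative only if the reasons for leaving subjects out are unrelated to the outcome. Here they may be closely related. A subject admitted for a device-related event, or explanted, is likely to miss scheduled visits or to have an emergency departure on record. A subject whose implant fails cannot follow the titration schedule. If such subjects leave the set, the MAE rate falls and the implant success rate rises because of the events those endpoints exist to count.

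If deviation records do not decide membership, then nothing written does. In an open-label, single-arm study the choice would be made with outcomes in view. That alternative needs no numerical assumption.

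At stake are the two primary endpoints of a first-in-human study, whose results are to be compared qualitatively with other devices (Synopsis, Statistical Model).

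**Working it through.** The plan has no figure to reproduce: the sample size of up to 10 is not derived, and 6.1 disclaims a power analysis. The checks below show what exclusion could do.

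**1. Effect on the MAE rate.** Suppose 10 subjects are enrolled and some with an MAE are excluded because of missed visits or emergency departures. The counts are illustrative. Intervals are exact (Clopper-Pearson) 95%.

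| All enrolled | After exclusion |
|---|---|
| 2/10 = 20% (2.5 to 55.6%) | one excluded: 1/9 = 11.1% (0.3 to 48.2%) |
| 2/10 = 20% (2.5 to 55.6%) | both excluded: 0/8 = 0% (0 to 36.9%) |
| 1/10 = 10% (0.3 to 44.5%) | one excluded: 0/9 = 0% (0 to 33.6%) |

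The intervals overlap heavily. The damage is to the reported rate and its upper limit, not to a test.

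**2. Effect on feasibility.** Section 6.3 defines the endpoint as technical success. Suppose the set were read as the technical successes named in 6.1. The per-protocol rate would then be 100% by construction. With 4 failures to implant (the most that the success rule in 6.1 allows) and the other six devices stimulating, all enrolled gives 6/10 = 60%, whereas the set gives 6/6 = 100%.

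**3. How small the set could become.** Assume that any recorded deviation excludes a subject, and that deviations occur independently with probability q at each of k contacts. The expected number remaining is 10 × (1 − q)^k. The documents give no q, so a range is shown.

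Contacts to Day 180:
- Visits 1 and 2, procedure, discharge and Day 14: 5.
- Named visits only (adding Days 30, 90 and 180): 8.
- Full schedule: 5, plus 2 × (30 − 14)/7 ≈ 5, plus (180 − 30)/7 ≈ 21, which gives 31. With a full four weeks of twice-weekly visits it is 5 + 8 + 20 = 33.
- Lighter schedule, assuming contacts go four-weekly after 12 weekly sessions: 12 sessions, 4 second weekly visits and 3 later contacts make 19 from Day 14. Adding the 4 contacts before Day 14 gives 23.

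| Contacts k | q = 1% | 2% | 5% | 10% |
|---|---|---|---|---|
| 5 (to Day 14) | 9.5 | 9.0 | 7.7 | 5.9 |
| 8 (named visits to Day 180) | 9.2 | 8.5 | 6.6 | 4.3 |
| 23 (lighter schedule) | 7.9 | 6.3 | 3.1 | 0.9 |
| 31 (Table 3 footnote) | 7.3 | 5.4 | 2.0 | 0.4 |

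For example, 10 × 0.98^31 = 5.4 and 10 × 0.95^31 = 2.0. Counts to 24 months are left out, because the primary endpoints fall at 6 months (safety) and at Day 14, or Day 14/21 in 4.2.2 (feasibility).

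**The case against.** The strongest reply is that 9.16 is a reporting rule. It requires departures to be recorded and nowhere says that one removes a subject from an analysis; the same holds for 4.35. Recording every departure in one class is not a fault in itself. This stands: the link between deviation records and the set is inferred, and the defect lies in 6.1.

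The second reply is that the harm is contained:
- The per-protocol analysis is additional, and 6.1 also promises an analysis of all enrolled subjects.
- Section 4.14 requires complete safety follow-up of everyone enrolled, and 4.35 requires all enrolled subjects to be accounted for.
- Section 7 sends all serious events to the DSMB.
- The safety part of the success rule (6.1) and of early termination (9.13) rests on DSMB judgement, not on a per-protocol rate.

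This stands in large part. It does not settle the matter, because 6.1 places intent-to-treat among the secondary analyses in one sentence and gives the primary analysis to technical successes in another.

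A reader might also infer stronger points that the documents do not support:
- **The set would be nearly empty.** This depends on assumed rates. At 1 to 2% per contact, about 5 to 7 of 10 remain at 6 months on the full schedule, and more if misses cluster within subjects. Section 3.2 gives a recharging interval of 1 to 4 weeks and 4.24 allows longer titration intervals, so the full schedule may overstate the contacts.
- **Harmed subjects will be excluded.** The text makes this possible, not certain.
- **The blood pressure result could shift by several mmHg.** Dropping the two worst of 10 responders raises the mean fall by 2.540/8 = 0.32 SD (expected normal order statistics), or 2.5 to 4.8 mmHg for an assumed SD of 8 to 15. This is a worst case; nothing ties those two subjects to deviations.

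**Conclusion.** The point holds in a limited form. Section 6.1 commits to a per-protocol analysis of the two primary endpoints and leaves the set undefined. Under either available reading (deviation records, or judgement made with open-label results in view), membership can depend on the outcome. In a study of up to 10 subjects, one or two exclusions can take an MAE rate of 20% to 11% or 0%.

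These figures rest on the illustrative event counts and on the inferred link to 9.16 and 4.35. That the set is undefined needs no assumption. The size of the set cannot be predicted from the documents. The study is descriptive and the events should still appear in the all-enrolled analysis, so the risk is a second, more favourable figure that could be given prominence. The change is worth making because it costs almost nothing.

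**What to change.** Before the first implant:

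1. In 6.1, delete the per-protocol analysis of the MAE and feasibility endpoints, and report both in all enrolled subjects.
2. Keep per-protocol only as a supportive analysis of the blood pressure endpoints, with a closed list of exclusions. For example, an unmet eligibility criterion removes the subject. An ambulatory recording not taken after observed therapy, or taken outside the visit window, removes that reading only.
3. State that none of the following excludes a subject: adverse events, emergency departures made to protect the subject, stimulation stopped for intolerance or harm, missed charging visits, and lost samples.
4. Cross-refer 9.16 to this list, so that it remains a reporting rule and is not read as defining the analysis set.

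The cost is a few sentences in 6.1 and 9.16, and the loss of a per-protocol safety and feasibility figure. No study procedure changes.
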